11.2.4. SECONDARY CRITERIA

The following analyses will be performed for each cohort, according to the matched treatment group:

- An estimation of the total hospital cost of each surgery procedure based on a top down micro-costing method performed during hospitalization stay;
- A description of the overall and specific urogenital healthcare consumptions during the 3 years of follow-up;
- A description of BPH re-treatment over the 3 years of follow-up (number of patients with a new BPH medication, number of patients hospitalized for BPH surgical procedure);
- A description of urinary symptoms (value of the IPSS, ISI, ICIQ-UI SF scores during the 1st year of follow-up and number of patients with hospitalization for urinary infection, for urinary retention, or for urethral stricture during the 3 years of follow-up);
- A description of the quality of life during the 1st year of follow-up using the IPSS-Q8 score, the Jenkins sleep questionnaire, the EQ-5D-5L questionnaire;
- A description of the recovery after surgery using the Quality of Recovery visual analogue score and the time before returning to normal professional activities;
- A description of the sexual side effects during the 1st year of follow-up using the IIEF15 and MSHQ-EjD questionnaire;
- A description of the associated complications (number and types).

[figure not shown]
A detailed analysis plan will be defined and will be validated by the steering committee of the study. Subsequent modifications must be made before the blinding is lifted on the database and will be systematically validated by the Scientific Council.

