	a description of the associated complications.		
	Comparisons between the PUL and the TURP/Laser cohorts and between the PUL and the SNDS cohorts will be performed after 1 year and 3 years of follow-up in a intention-to-treat analysis using:		
	o a linear regression model when it involves quantitative variables,		
	 a logistic regression model adjusted on potential confounding when it involves qualitative variables. 		
EXPECTED IMPACTS	Results of the study will be used to support French market release, reimbursement, and clinical acceptance of the Urolift system in France.		

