3.2. SECONDARY OUTCOMES MEASURES

Secondary endpoints will be:

- The incremental cost/Qaly of PUL compared to transurethral surgery at 12 months
- The total hospital cost of each surgery procedure based on a top down micro-costing method performed during hospitalization stay
- Overall and specific urogenital healthcare consumptions at 4 months, 1 year and 3 years following the surgical procedure
 - Dispensed medications identified using the corresponding codes of the Anatomical Therapeutic Chemical (ATC) Classification;
 - o In- and out-patient visits;
 - Hospitalisation and their corresponding discharge diagnoses coded according to International Classification of Disease, 10th revision;
 - Medical procedures;
 - Nursing acts and physiotherapy;
 - Medical imageries and lab tests;
 - Transport;
 - Sick allowances;
 - At 4 months: all healthcare consumptions which are not reimbursed, but payed by the patient (e.g.: urinary incontinence products).

• BPH retreatment,

• Any dispensing of the following medications at 1 and 3 years after surgical procedure: alpha-blockers (ATC code G04CA) or 5-alpha-reductase inhibitors (ATC code G04CB);

 Hospitalization at 1 and 3 years after surgical procedure, with the main diagnosis of BPH (ICD-10 code N40) and the surgical procedure codes JGNE003, JGNE171, JGNJ001, JGFA005 JGFA009, JGFA015, JGFE023, JGFE365.

Urinary symptoms,

- Urinary incontinence evolution between inclusion and 4 months after surgical procedure (Incontinence Severity Index (ISI));
- International consultation on Incontinence questionnaire for Urinary incontinence short form (ICIQ-UI SF)
- Hospitalization with a discharge diagnosis ICD-10 code related to an urinary infection (code N41 for acute prostatitis or code N10 for acute pyelonephritis) at 1 and 3 years after surgical procedure;
- Hospitalization with a discharge diagnosis ICD-10 code related to urinary retention (R33) at 1 and 3 years after surgical procedure;
- Hospitalization with a discharge diagnosis ICD-10 code and/or medical procedure related to urethral stricture at 1 and 3 years after surgical procedure.

• Global quality of life,

- IPSS and IPSS-Q8 evolution between inclusion, 4 month, and 1 year after surgical procedure;
- O Jenkins sleep questionnaire between inclusion, 4 months, and 1 year after surgical procedure;
- EQ-5D-5L questionnaire (appendix 2) evolution between inclusion, 4 months, and 1 year after surgical procedure;

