• The time to complete recovery and to return to normal professional activities

- Recovery after surgery (Quality of Recovery visual analogue score (QoR VAS)) at 1, 2, 3 and 4 months after surgical procedure;
- Time before returning to professional activities.

• Sexual side effects,

• Sexual quality of life evolution between inclusion, 4 months and 12 months after surgical procedure (IIEF15, Male Sexual Health Questionnaire for Ejaculatory Dysfunction (MSHQ-EjD).

Associated complications,

• Clavien Dindo classification of adverse events at 4 months after surgical procedure.

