11.2. STATISTICAL METHODS EMPLOYED

11.2.1. GENERALITIES

Statistical analysis will be performed using SAS® software (SAS Institute, latest current version, North Carolina, USA). Qualitative and ordinal variables will be summarized by frequencies and proportions of each modality, taking into account missingness as a modality. Continuous variables will be summarized by size, number of patients with missing data, arithmetic mean, standard deviation, median, interquartile ranges and extreme values. Confidence intervals will be estimated using Normal approximation for quantitative and qualitative relevant parameters, or bootstrapping method for costs when count < 100 patients.

Standardized mean differences (*Rosenbaum*, *Rubin*, 1985) will be estimated to measure the effect size of quantitative and qualitative baseline characteristics between groups (PUL and TURP cohorts, matched patients of PUL and SNDS cohorts).

For confidence intervals, 2-sided confidence level of 95% will be used. For all tests, a 2-sided significance level of 5% will be used:

- Proportions will be compared between two independent groups using Pearson's Chi-2 test (or Fisher's exact test when expected counts are < 5)
- Means will be compared between two independent groups using Student's t-test when normal distribution is followed (or Mann-Whitney's test when normal distribution is not followed)
- Occurrence of events (retreatment, urinary symptoms) will be estimated across time using Kaplan-Meier estimator and compared between groups with logrank test.
- Adjusted comparisons between PUL and the TURP/Laser cohorts and between PUL and SNDS cohorts will be
 performed in intention-to-treat analysis using linear regression model when it involves quantitative variables,
 and using logistic regression model adjusted on potential confounders when it involves qualitative variables.

[figure not shown]
A Statistical Analysis Plan (SAP) will be developed and will be validated before the analyses.

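### IPSS and ISI are changes from inclusion in section 3.2 but score values in section 11.2.4, the ISI time window differs, and the protocol does not name the inclusion score as a covariate in the linear model

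*Protocol*

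**What the plan says.** **Endpoint definitions (protocol, section 3.2).** IPSS appears under global quality of life as "IPSS and IPSS-Q8 evolution between inclusion, 4 month, and 1 year after surgical procedure". ISI appears under urinary symptoms as "Urinary incontinence evolution between inclusion and 4 months after surgical procedure", with no later time point. EQ-5D-5L and the sexual scores are worded like IPSS: "EQ-5D-5L questionnaire (appendix 2) evolution between inclusion, 4 months, and 1 year after surgical procedure" and "Sexual quality of life evolution between inclusion, 4 months and 12 months after surgical procedure". ICIQ-UI SF is named with neither a form nor a time point.

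**Analysis (section 11.2.4).** IPSS is now among the urinary symptoms, and the item to be described is the "value of the IPSS, ISI, ICIQ-UI SF scores during the 1st year of follow-up". For the quality-of-life and sexual scores this section names the questionnaires without saying value or change.

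**Time points elsewhere.** Section 2.2 sets urinary symptoms at both 4 months and 1 year, and section 9.7 has ISI completed at the month 12 visit.

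**Comparison of cohorts.** Section 11.2.1 gives a t-test or Mann-Whitney test for means. It then introduces adjusted comparisons, "using linear regression model when it involves quantitative variables" and a logistic model for qualitative ones; mention of confounders follows the logistic model. The data analysis part of the synopsis lists "a linear regression model when it involves quantitative variables" with no adjustment attached, and again ties confounders to the logistic model alone. No covariate is named for the linear model.

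**The concern.** A programmer who follows section 3.2 compares change in IPSS and ISI. One who follows section 11.2.4 compares score values. No section says which form enters the comparison in section 11.2.1, and for ISI the month 12 result is either an endpoint or not.

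The form matters because the cohorts are self-selected. Section 1.3 relies on matching and statistical adjustment to make up for the lack of randomisation. Matching cannot help these scores: it applies to the SNDS cohort (section 5.2.3), and section 1.3 acknowledges that the SNDS holds no functional results. The score comparisons rest on the regression between the PUL and TURP/laser cohorts alone.

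If that regression does not contain the inclusion score, a baseline difference enters the two forms with opposite signs. A modest difference in symptom relief between the procedures could then change direction with the section that is programmed.

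**Working it through.** **The plan's own figure.** The protocol states no power for the scores; the only related figure is the precision of a mean in section 11.1. Half-width relative to the mean = 1.96 x CV / sqrt(n). With n = 80, CV 0.6 gives 13.15% and CV 1.2 gives 26.3%. This reproduces the stated 13% to 26%. It concerns one cohort mean, so it does not settle the form of the comparison.

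**The two forms without baseline adjustment.** Let B be the inclusion score and Y the follow-up score.

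- Value difference: D_v = mean(Y, PUL) - mean(Y, TURP/laser).
- Change difference: D_c = mean(Y - B, PUL) - mean(Y - B, TURP/laser) = D_v - D_b, where D_b is the baseline difference.

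So D_v - D_c = D_b exactly, for the same patients. With other covariates but not B in the model, the gap is the baseline difference adjusted for those covariates. With B in the model the gap is zero, because subtracting B from the outcome alters only the coefficient of B.

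**Size.** From the protocol: 80 per cohort, two-sided 5%, and a standardised difference of 10% as the imbalance flag (section 11.2.2). Assumed: SD 1 at both visits, no cohort effect given baseline, correlation r from 0.3 to 0.7, and a systematic baseline difference d of 0.1 or 0.3 SD. Then:

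- expected D_v = r x d, with SE = sqrt(2/80) = 0.158;
- expected D_c = (r - 1) x d, with SE = sqrt(2 x 2(1 - r)/80), which is also 0.158 at r = 0.5.

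At d = 0.3 and r = 0.5, D_v = +0.15 and D_c = -0.15. Each is shifted by 0.15/0.158 = 0.95 SE. The rejection rate is P(Z > 1.96 - 0.95) + P(Z < -1.96 - 0.95), about 16%. Simulation with 1,500 runs per row gave:

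| d | r | value estimate | change estimate | false rejection: value | change | with baseline in model |
|---|---|---|---|---|---|---|
| 0.1 | 0.3 | 0.032 | -0.068 | 5.5% | 6.2% | 5.3% |
| 0.1 | 0.5 | 0.052 | -0.045 | 7.3% | 5.6% | 4.9% |
| 0.1 | 0.7 | 0.068 | -0.035 | 7.5% | 5.4% | 5.1% |
| 0.3 | 0.3 | 0.084 | -0.216 | 8.0% | 22.7% | 5.3% |
| 0.3 | 0.5 | 0.153 | -0.146 | 14.7% | 14.5% | 4.6% |
| 0.3 | 0.7 | 0.212 | -0.089 | 25.6% | 10.1% | 4.9% |

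In every run the value and change models with baseline included gave the same cohort effect, apart from rounding error of about 1e-15.

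**Is 0.3 SD plausible?** By chance alone, the baseline standardised difference has SE 0.158 and a 95% range of about +/-0.31. A single dataset can therefore show a gap of that size between the two forms even if the cohorts come from the same population. Chance imbalance does not raise the error rate averaged over repetitions: at d = 0 the simulated rates were 4% to 6%. The raised rates in the table need a systematic difference. If the IPSS SD is 5 to 7 points (an assumption; the protocol gives none), 0.1 SD is 0.5 to 0.7 points and 0.3 SD is 1.5 to 2.1 points.

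**Precision.** With baseline in the model at r = 0.5, residual variance is 1 - 0.5^2 = 0.75 of the value analysis. Imbalance of 0.3 SD costs a factor 1 + 0.3^2/4 = 1.0225, so SE = sqrt(2 x 0.75 x 1.0225/80) = 0.138 against 0.158.

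**The case against.** Five points can be made on the other side.

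- **Section 11.2.4 describes; it does not compare.** Showing values by visit is compatible with an endpoint defined as evolution from inclusion. This stands in part. Still, section 11.2.4 is where the analysis gives these scores a form, and nothing else says which form is compared. The ISI window also differs on any reading.
- **Baseline adjustment may be planned.** A reader might infer that neither analysis conditions on the baseline score. The documents do not support that: section 11.2.1 announces adjusted comparisons, and a covariate list may properly be left to the SAP, which is not shown. What stands is that the score is not named and that the synopsis and section 11.2.1 differ on whether the linear model is adjusted.
- **Most scores do not conflict.** A reader might extend the value/change conflict to all symptom, quality-of-life and sexual scores. It covers only IPSS and ISI. ICIQ-UI SF has no stated form in section 3.2, and for the others section 11.2.4 is silent on form.
- **The simulation favours baseline adjustment by construction.** It assumes no effect given baseline. If the cohorts differed stably and would change in parallel, the unadjusted change would be unbiased and the baseline-adjusted estimate would not (Lord's paradox). This stands: it cannot be claimed that change over-corrects, only that the forms disagree.
- **Stakes are limited.** The primary endpoint is cost per avoided complication, and section 1.6 says that re-testing clinical effectiveness is not the aim. This too stands.

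**Conclusion.** The point holds for IPSS and ISI. Their form differs between sections 3.2 and 11.2.4. The month 4 limit for ISI in section 3.2 also disagrees with section 11.2.4, with the objective in section 2.2 and with the month 12 collection in section 9.7. Separately, the synopsis and section 11.2.1 leave it unclear whether the linear model is adjusted.

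The gap between the two forms equals the full baseline difference only when neither that score nor other covariates are adjusted for. The false rejection rate of about 15% rests on an assumed systematic imbalance of 0.3 SD, correlation 0.5 and no effect given baseline. At the imbalance the protocol itself flags, 0.1 SD, the unadjusted forms differ by 0.10 SD and the error rate barely moves. These are secondary endpoints, but they bear on the trade-off between symptom relief and side effects set out in sections 1.4 and 1.5. The correction is worth making before the scores are analysed.

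**What to change.** - In sections 3.2 and 11.2.4, give each symptom, quality-of-life and sexual score one form and the same time points, months 4 and 12. Bring ISI into line and give ICIQ-UI SF a form and time points.
- Reword the synopsis to agree with section 11.2.1 that the linear model is adjusted.
- Name the inclusion value of the same score as a covariate in that model, beside the other confounders. The choice between value and change then no longer affects the cohort effect.
- Report raw values and raw changes by visit as description only.
- State that, in non-randomised cohorts, baseline adjustment reduces confounding but does not guarantee its removal.

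The cost is wording in the protocol and SAP. No new data are needed: sections 9.2 and 9.3.2 already have these questionnaires completed at inclusion, and sections 9.6 and 9.7 at months 4 and 12.

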12. STUDY SUPERVISION

12.1. STEERING COMMITTEE

12.1.1. COMPOSITION

A steering committee will supervise the running of the study. The steering committee will be responsible for monitoring the progress of the study towards its objectives, and ensuring adherence to the protocol and local regulations as well as subject safety. The steering committee will include the Project Coordinator ([name]), the Scientific Coordinator ([name]), methodologist ([name]), economist ([name]), representatives from relevant fields according to the nature of the research, and sponsor representative.

12.1.2. FREQUENCY OF MEETINGS

The Scientific Research Council will meet to be defined according to the needs of the study and at least once per year.

12.1.3. Function

Its goal is to make all important decisions at the request of the coordinating investigator concerning the proper implementation of the research and following protocol.

It checks that ethics are respected.

It keeps up to date with the research progress, possible issues and available results via the coordinating team and coordinating investigator research center.

It makes decisions on all necessary protocol amendments for the research project, in particular:

- Measures facilitating recruitment for the research project,
- Changes to the protocol prior to their presentation to the CPP and the competent health authority,
- Decisions to open or close sites participating in the research,
- Measures that guarantee the highest level of safety of the participants (including changes in information sheets and consent documents),
- Discussion of the results and the approach to their publication.

The steering committee can suggest prolonging or interrupting the research if the recruitment rate is too slow, the loss to follow-up is too high, or major protocol violations have occurred, as well as for medical and/or administrative reasons. The steering committee specify the possible terms for prolonged monitoring of the participants included in the research.

If the participating individuals suggest carrying out new biological research studies using the research material and when these have not been laid out in the protocol, the Scientific steering committee studies them and sets the information conditions of the participants, data access and result publication rules.

At the conclusion of the meeting, the president of the steering committee must inform the sponsor of the decisions that have been made. Decisions concerning a major change to the science or budget change must be approved by the sponsor.

13. RIGHTS OF ACCESS TO DATA AND SOURCE DOCUMENTS

13.1. ACCESS TO DATA

Agreeing to participate in the protocol implies that the investigators will make the documents and personal data that are strictly necessary for the monitoring, quality control and auditing of the research, available in accordance with the laws and regulations in force.

13.2. SOURCE DATA

All information contained in original documents, or in authenticated copies of these documents, relating to clinical examinations, observations or other activities conducted as part of a research study and necessary for the reconstitution and evaluation of the research. The documents in which the source data are saved are called the source documents.

13.3. DATA CONFIDENTIALITY

In accordance with the legislative provisions in force, persons having direct access to source data will take all the necessary precautions to ensure the confidentiality of information relating to investigational medicinal products, research, participants, especially as regards their identity and the results obtained. These people, like the investigators, are subject to professional secrecy.

During or at the end of the research, the data collected on the participants and sent to the sponsor by the investigators (or any other specialised contributor) will made anonymous. The data must never explicitly mention the names of the persons concerned or their addresses.

Each patient will be assigned a confidential identification code, consisting of the number of the investigation center (2 digits) and a patient number (3 digits) and a code letter (3 letters). The code letters may be constructed from the initials of the name and surname of the patient.

The sponsor will ensure that each participant has given his/her written agreement for access to the individual data concerning them and strictly necessary for the quality control of the research.

14. QUALITY CONTROL AND QUALITY ASSURANCE

14.1. GUIDELINES FOR COLLECTING DATA

All the information required by the protocol must be recorded in case report forms and an explanation must be provided for any missing data. The data must be collected as and when they are obtained, and transcribed in these notebooks in a clear and legible way.

Clinical and economic data, all data will be collected on electronic CRF (e-CRF), and specific auto-questionnaire.

14.2. QUALITY CONTROL

A clinical researcher appointed by the sponsor will regularly visit each center investigator, during the implementation of the research, one or more times during research according to the frequency of the inclusions and at the end of the research. During these visits, and in accordance with the risk-based monitoring plan (participant, logistics, impact, resources), the following elements will be reviewed:

- informed consent,
- compliance with the research protocol and the procedures defined therein,
- quality of the data collected in the case report form: accuracy, missing data, consistency of the data with the source documents (medical records, appointment books, originals of laboratory results, etc.).

All visits will be the subject of a monitoring report by written report.

14.3. DATA MANAGEMENT AND SNDS LINKAGE

For each included patient, all clinical and economic data will be collected by the BPE research platform using an e-CRF and a self-administered questionnaire. A specific database will be developed for this study using standard tools (input dataset using MySQL, and data entry web application via Grails) in accordance with the General Data Protection Regulation (GDPR). It will allow an on-line data entry and remote by internet. This database will be tested before any data input. Database access will be restricted to authorized personnel, using state-of-the-art security techniques. A data validation plan will be developed and will describe in detail the controls to be made for each variable (coherence of dates and intervals, coherence of conditional variables, invalid values, boundaries, missing data, respect of criteria predefined in the protocol, etc.).

All clinical and economic data will constitute the dataset [Prostatic_Surgery], which will also include the confidential identification number allocated to each patient, as described in the §13.3.

Two methods may be used to link data from the dataset [Prostatic_Surgery] to those of the SNDS: the direct linkage, for which patient NIR national identifier is required, and the probabilistic linkage, which allows identifying eventually patients not found with the previous method.

i. Direct linkage

To link directly patient data to SNDS data, the patient NIR national identifier will be requested directly to the patient through the consent form. Once the NIR recovered, the BPE research platform will create a table separate from the dataset [Prostatic_Surgery], which will include the NIR, the confidential identification number, the birth date and the sex of each patient of the study. The BPE research platform will transmit this table to the CNAM using the online SAFE application. Based on the data forwarded, the CNAM will generate a pseudo anonymized SNDS identification code through it own 3-step anonymization procedure to make possible the extraction of the required SNDS data for the patients concerned.

ii. Probabilistic linkage

For probabilistic linkage, the BPE research platform will create a table separate from the dataset [Prostatic_Surgery], which will include for each patient, the confidential identification number and the data that are common to the dataset [Prostatic_Surgery] and the SNDS database. These data are listed below:

- birth date;
- city of residence;
- hospital identifier (FINESS);
- date of hospitalization for the prostatic procedure;

- procedure codes of the prostatic procedure performed during the hospitalization.

This table will be encrypted and deposited on the secured platform of the CNAM, according to the CNAM or Health DataHub procedures in force.

Based on data of the table provided by the BPE research platform, the CNAM will search in the SNDS the corresponding patients and will develop a targeting algorithm relevant for answering the study requirements. This algorithm will require applicant approval before any extraction.

[figure not shown]

Figure to illustrate the process of linkage between patient data and SNDS data

[figure not shown]
In both cases, the CNAM will extract the required data (sociodemographic characteristics, date of death, LTD registration, outpatient reimbursed healthcare expenditures, hospital-discharge summaries and the corresponding costs).

The SNDS database extraction criteria will be described in a Data Extraction Plan (DEP) approved prior to initiating extraction. After data extraction, the CNAM will provide the requested SNDS data and the confidential patient identification number to the BPE research platform through dedicated networks ensuring a private and secured data transfer. The dataset [Prostatic_Surgery] and SNDS data will be merged by the BPE team using the confidential patient identification number. After data integration and validation, the table used for data linkage will be deleted and a new identification number will be created randomly for each patient of the study.

Data transformation, including decision rules, disease definition, exposure definition, outcomes, risk factors, healthcare resources and calculated variables will be detailed in a data management plan (DMP). Raw data and transformed data will be stored on a network meeting security standards as required by the French law:

- order of 22 March 2017 relating to the security reference system applicable to the National Health Data System (SNDS, 2017)
- SNDS security standards (available on: https://www.snds.gouv.fr/SNDS/Protection-de-la-donnée)

Data management programs will be developed with SAS® software (SAS Institute, latest current version, North Carolina, USA). After verification and resolution of incoherencies, the database will be locked for extraction and statistical analysis.

